1 GLOSSARY OF TERMS

Names of test product(s)	Throughout this document, test product(s) will be referred to as [REDACTED] soft contact lenses or [REDACTED] contact lenses [REDACTED].
Name of Control Product(s)	CooperVision® BIOFINITY® (comfilcon A) soft contact lenses
Adverse Device Effect (ADE)	Adverse event related to the use of an investigational medical device (test product) or control product. Note: This definition includes adverse events resulting from insufficient or inadequate instructions for use, deployment, implantation, installation, or operation; any malfunction; and use error or intentional misuse of the test product or control product.
Adverse Event (AE)	Any untoward medical occurrence, unintended disease or injury, or untoward clinical signs (including abnormal laboratory findings) in subjects, users or other persons, whether or not related to the investigational medical device (test product). Note: For subjects, this definition includes events related to the test product, the control product, or the procedures involved. For users or other persons, this definition is restricted to events related to the test product. Requirements for reporting Adverse Events in the study can be found in Section 11.
Anticipated Serious Adverse Device Effect	Serious adverse device effect which by its nature, incidence, severity, or outcome has been identified in the risk management file.
Device Deficiency	Inadequacy of a medical device with respect to its identity, quality, durability, reliability, safety, or performance. Note: This definition includes malfunctions, use errors, and inadequate labeling.

	Requirements for reporting Device Deficiencies in the study can be found in Section 11.
Enrolled Subject	Any subject who signs an informed consent form for participation in the study.
Interventional Clinical Trial	A research trial that prospectively assigns, whether randomly or not, human participants or groups of humans to one or more health-related interventions to evaluate the effects on health outcomes, and/or a research trial in which diagnostic or monitoring procedures beyond standard of care are conducted and generate outcomes for use in analysis of data.
Investigational Product	Is defined as a preventative (vaccine), a therapeutic (drug or biologic), device, diagnostic, or palliative used as a test or control product in a clinical trial, including a product with a marketing authorization when used or assembled (formulated or packaged) in a way different from the authorized form, or when used for an unauthorized indication, or when used to gain further information about the authorized form.
Malfunction	Failure of a medical device to perform in accordance with its intended purpose when used in accordance with the instructions for use or clinical investigation plan.
Non-serious Adverse Event	Adverse event that does not meet the criteria for a serious adverse event.
Randomized Subjects	Any subject who is assigned a randomized treatment.
Serious Adverse Device Effect (SADE)	Adverse device effect that has resulted in any of the consequences characteristic of a serious adverse event.
Serious Adverse Event (SAE)	Adverse event that led to any of the following: 
 • Death.

	
• A serious deterioration in the health of the subject that either resulted in:
a. a life-threatening illness or injury. Note: Life-threatening means that the individual was at immediate risk of death from the event as it occurred, ie, it does not include an event which hypothetically might have caused death had it occurred in a more severe form.b. any potentially sight-threatening event or permanent impairment to a body structure or a body function.c. in-patient hospitalization or prolonged hospitalization. Note: Planned hospitalization for a pre-existing condition, without serious deterioration in health, is not considered a serious adverse event. In general, hospitalization signifies that the individual remained at the hospital or emergency ward for observation and/or treatment (usually involving an overnight stay) that would not have been appropriate in the physician's office or an out-patient setting. Complications that occur during hospitalization are adverse events. If a complication prolongs hospitalization or fulfills any other serious criteria, the event is serious. When in doubt as to whether "hospitalization" occurred, the event should be considered serious.d. a medical or surgical intervention to prevent a) or b).e. any indirect harm as a consequence of incorrect diagnostic test results when used within manufacturer's instructions for use.
--	---

	
 • Fetal distress, fetal death, or a congenital abnormality or birth defect. 
Refer to Section 11 for additional SAEs.

Significant Non-Serious Adverse Event
	
Is a symptomatic, device-related, non-sight threatening adverse event that warrants discontinuation of any contact lens wear for greater than or equal to 2 weeks.
 
Refer to Section 11 for additional Significant Non-Serious AEs.

Unanticipated Serious Adverse Device Effect
	
Serious adverse device effect which by its nature, incidence, severity or outcome has not been identified in the risk management file.

Use Error
	
Act or omission of an act that results in a different medical device response than intended by manufacturer or expected by user. Note: This definition includes slips, lapses, and mistakes. An unexpected physiological response of the subject does not in itself constitute a use error.

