10.2.4 Adverse Event Collection: Safety Assessment

Assess and record any AEs that are observed or reported, including those associated with changes in concomitant medication dosing since the previous visit. Requirements for reporting AEs in the study can be found in Section 11.

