11 ADVERSE EVENTS AND DEVICE DEFICIENCIES

11.1 General Information

An AE is any untoward medical occurrence, unintended disease or injury, or untoward clinical signs (including abnormal laboratory findings) in subjects, users, or other persons, whether or not related to the investigational medical device (test article). Refer to the Glossary of Terms and figures below for categories of AEs and SAEs.

Figure 11–1 Categorization of All AEs

[figure not shown]
[figure not shown]

Figure 11–2 Categorization of All SAE

SAEs

In addition to reporting all AEs (serious and non-serious) meeting the definitions, the Investigator must report any occurrence of the following as an SAE:

- An ocular infection including a presumed infectious ulcer with any of the following characteristics:
 - Central or paracentral location
 - Penetration of Bowman’s membrane
 - Infiltrates > 2 mm diameter
 - Iritis
 - Increase in intraocular pressure
 - Culture positive for microorganisms
 - Increasing size or severity at subsequent visits
- Any central or paracentral corneal event (such as neovascularization) that results in permanent opacification

- Hypopyon
- Hyphema
- Neovascularization within the central 6 mm of the cornea
- Permanent vision loss as defined by loss of 2 or more lines of BCVA from enrollment visit that fails to resolve
- Uveitis (anterior, intermediate, or posterior)
- Corneal abrasion affecting $\geq 50\%$ of corneal surface area

Significant Non-Serious AE

A significant non-serious AE is a device-related, non-sight threatening AE that warrants discontinuation of any contact lens wear for greater than or equal to 2 weeks. In addition, the Investigator must report any occurrence of the following as a Significant Non-Serious Adverse Event:

- Peripheral non-progressive non-infectious ulcers
- All symptomatic corneal infiltrative events
- Corneal staining score greater than or equal to Grade 3 [REDACTED]
- Temporary vision loss as defined by loss of 2 or more lines of BCVA from enrollment visit that persists for 2 or more weeks
- Neovascularization score greater than or equal to Grade 2 [REDACTED]

[REDACTED]

Device Deficiencies

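### Does it matter that the Glossary requires a significant non-serious AE to be symptomatic while Protocol Section 11.1 does not?

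*Protocol*

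**What the plan says.** The Protocol Glossary (Section 1) defines the category as follows: "Is a symptomatic, device-related, non-sight threatening adverse event that warrants discontinuation of any contact lens wear" for at least 2 weeks. It then adds "Refer to Section 11 for additional Significant Non-Serious AEs".

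Protocol Section 11.1 restates the definition: "A significant non-serious AE is a device-related, non-sight threatening AE that warrants discontinuation of any contact lens wear", again for at least 2 weeks. It follows this with a list that investigators must report in the category. Five items are visible:

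- peripheral ulcers that are neither progressive nor infectious
- "All symptomatic corneal infiltrative events"
- "Corneal staining score greater than or equal to Grade 3"
- temporary loss of 2 or more lines of best corrected acuity lasting 2 weeks or more
- neovascularization of Grade 2 or more

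On how the sections relate, the Glossary entry for adverse events says "Requirements for reporting Adverse Events in the study can be found in Section 11", and Section 10.2.4 says "Requirements for reporting AEs in the study can be found in Section 11". Section 11.1 points the other way: "Refer to the Glossary of Terms and figures below for categories of AEs and SAEs".

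The category is used in two places. Protocol Section 12.6 says these events will be identified. SAP Section 5.3.1 says the ocular ones will be noted. The SAP takes its definition of an adverse event from the Protocol and shows no separate definition of this category.

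**The concern.** Two definitions of one term differ by a qualifying condition, and a site can follow either and be within the Protocol. Consider a sign found on slit-lamp examination without any complaint from the subject, related to the lens, not threatening sight, and serious enough to stop lens wear for 2 weeks. Section 11.1 puts it in the category and the Glossary leaves it out.

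Such events are conceivable. The Protocol's definition of an adverse event includes clinical signs, and biomicroscopy is done at every study visit. An asymptomatic corneal infiltrate is the natural example, because the list covers infiltrative events only when they are symptomatic. With about 14 to 17 sites classifying events, similar findings could be flagged at one site and not at another. The SAP would carry that inconsistency into the report, since it has no definition of its own to settle the matter. What would be at stake is the reproducibility of a safety flag.

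**Working it through.** No arithmetic applies beyond counting list items. The check is to apply both definitions to each kind of event and then follow the event into the planned outputs.

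**Step 1. Shared conditions.** Both texts require that the event is related to the device, does not threaten sight, and warrants at least 2 weeks without lens wear. The Glossary alone adds symptoms.

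**Step 2. Classification by type of event.**

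| Type of event | Glossary | Section 11.1 |
|---|---|---|
| On the Section 11.1 list, symptomatic or not as the item specifies | In | In |
| Unlisted, shared conditions met, symptomatic | In | In |
| Unlisted, shared conditions not all met | Out | Out |
| Unlisted, shared conditions met, asymptomatic | Out | In |

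Listed events agree because the Glossary accepts Section 11's additional events. Only the last row differs.

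**Step 3. What the list leaves for that row.** One of the 5 visible items names symptoms (infiltrative events). The other 4 do not, so qualifying ulcers, Grade 3 staining, Grade 2 neovascularization and persistent acuity loss are flagged under both texts even without symptoms. What remains is an unlisted, symptomless sign that still warrants 2 weeks out of lenses. The documents give no rate for such events and do not show that an asymptomatic infiltrate would meet the 2-week condition.

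**Step 4. What happens to an event in that row.**

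- It is an adverse event under either text, and Protocol Section 12.6 accounts for all adverse events from consent to exit.
- It is device-related by construction, so it meets the Glossary definition of an adverse device effect. Protocol Section 11.3 requires documentation on the dedicated form within 24 hours, with severity, treatment, outcome, seriousness and causality.
- SAP Section 5.3.1 tabulates it by Preferred Term, shows its relationship to the lens in all adverse event tables, and marks it in the listings if it led to study discontinuation.
- The significant non-serious flag is the only classification that depends on the choice of definition.

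**Step 5. What uses the flag.** The visible text says these events will be identified (Protocol 12.6) or noted (SAP 5.3.1). The planned counts and percentages are by Preferred Term. No visible text plans a count or rate for the category itself. Both documents state that there are no safety hypotheses, and Protocol 12.6 rules out inferential testing for safety.

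**The case for a change.** The best case for a correction is that the conflict is plain in the text, the two versions give opposite answers for an event that can be described exactly, and aligning the wording would be cheap. The cross-references do not clearly resolve it. One can argue that the Glossary governs, because Section 11.1 sends the reader there for categories while the pointers to Section 11 concern reporting requirements and additional events. That reading is workable, but it is an inference: Section 11.1 restates the base definition in altered form before adding its list, and no precedence clause is visible. The list does not show intent either, since one item requires symptoms and others rest on a sign or grade alone.

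All of that stands as a description of the mismatch. It does not show a consequence. The strongest practical argument, inconsistent flagging across sites, concerns a label on events that are fully reported in any case, and no such event has been shown to be likely.

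There is also a limit on what can be claimed. Figure 11-1, which Section 11.1 names as a source for the categories, could not be read, and parts of Section 11 are redacted. A clarification may exist there. The two visible definitions would still differ, but the claim that classification is unresolved cannot be made with full confidence.

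**Conclusion.** The two definitions do differ by one word, and the visible text sets no order of precedence. No change to the plan follows, because nothing would be gained in the analysis. The difference touches only asymptomatic, unlisted events that meet all the shared conditions, a set of unknown size that may be empty. For any such event the record, the 24-hour documentation, the Preferred Term tabulation and the stated relationship to the lens are the same under either text. Only a descriptive flag could differ, and no visible planned count, estimate, test or conclusion rests on it.

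This rests on two assumptions: that the redacted parts of the plan contain no summary or decision rule built on this category, and that sites document device-related events as Protocol Section 11.3 requires. It takes no view on which definition is the right one.

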2 LIST OF ACRONYMS AND ABBREVIATIONS

Table 2-1 List of Acronyms and Abbreviations Used in This Protocol

Abbreviation	Definition
ADE	Adverse device effect
AE	Adverse event
BCVA	Best corrected visual acuity
Biofinity contact lens or Biofinity	CooperVision® BIOFINITY® (comfilcon A) soft contact lenses
CFR	Code of Federal Regulations
CI	Confidence interval
CLCDVA	Contact lens corrected distance visual acuity
CLEAR CARE	CLEAR CARE Cleaning & Disinfecting Solution
CRF	Case report form
CSM	Clinical site manager
CTT	Clinical trial team
D	Diopter(s)
D/C	Discontinue
DEP	Deviations and evaluability plan
eCRF	Electronic case report form
EDC	Electronic data capture
FAS	Full analysis set
FDA	US Food and Drug Administration
GCP	Good Clinical Practice
IB	Investigator's brochure
ICF	Informed consent form
ICH	International Council for Harmonisation of Technical Requirements for Pharmaceuticals for Human Use
IEC	Independent ethics committee
IP	Investigational product
IRB	Institutional review board
ISO	International Organization for Standardization
LID	Lens identification
logMAR	Logarithm of the minimum angle of resolution
N/A	Not applicable

Abbreviation	Definition
OD	Right eye
OS	Left eye
OU	Both eyes
PP	Per protocol analysis set
[REDACTED]	[REDACTED]
[REDACTED]	[REDACTED]
SAE	Serious adverse event
SADE	Serious adverse device effect
SD	Standard deviation
SiHy	Silicone hydrogel
SOP	Standard operating procedure
[REDACTED]	[REDACTED]
[REDACTED]	[REDACTED]
US / USA	United States of America
USV	Unscheduled visit
VA	Visual acuity
vs	Versus

3 PROTOCOL SUMMARY

This will be a prospective, randomized [REDACTED] controlled, double-masked, parallel-group clinical study.

Approximately 14-17 sites in the US will enroll approximately 252 subjects. [REDACTED] Subjects will be expected to attend 4 office visits: Screening / Baseline / Dispense, Week 1 Follow-up, Month 1 Follow-up, and Month 3 Follow-up/Exit. The total expected duration of participation for each subject is approximately 3 months in this daily wear clinical study. Accounting for both screen failure and dropout rates, approximately 152 subjects will be assigned to wear the test lenses and 76 subjects will be assigned to wear the control lenses, [REDACTED]

[REDACTED]

Subjects and the study personnel conducting the study evaluations will be masked to treatment. Subjects who meet the inclusion and exclusion criteria will be randomized to wear either the test contact lenses [REDACTED] in both eyes or the control contact lenses (Biofinity) in both eyes for 3 months of daily wear exposure.

[REDACTED]

[REDACTED]

At the Screening / Baseline / Dispense Visit, study lenses will be dispensed to qualified subjects [REDACTED]

All study lenses will be worn for at least 5 days per week and 8 hours per day in a daily wear modality (eg, will not be worn while sleeping).

[Redacted]

[Redacted]

[Redacted]. Regardless of whether the subject is randomized to the test or the control group, CLEAR CARE® Cleaning & Disinfecting Solution (CLEAR CARE) must be used for cleaning and disinfection.

[Redacted]

[Redacted]

[Redacted]

Investigational product type	Medical Device
Study type	Interventional
Investigational products	Test Product: [Redacted] soft contact lens Control Product: Biofinity soft contact lens
Purpose and rationale	The purpose of this clinical study is to demonstrate the safety and performance of the investigational [Redacted] soft contact lens compared to the commercially available Biofinity soft contact lens, when worn in a daily wear modality, by assessing visual acuity as the primary endpoint.
Objective(s)	The primary effectiveness objective is to demonstrate noninferiority [Redacted] compared to Biofinity in CLCDVA at Week 1 Follow-up.

	
 █ [REDACTED] █ [REDACTED] █ [REDACTED] █ [REDACTED] █ [REDACTED] 
Safety
 
 • AEs • Biomicroscopy • Device deficiencies
Study Design	
This will be a prospective, randomized, [REDACTED] [REDACTED] controlled, double-masked, parallel-group, daily wear clinical study. Subject participation in the study will be approximately 14 weeks with approximately 3 months of exposure to study lenses.

Subject population	
Volunteer subjects aged 18 or over who are adapted daily wear frequent replacement soft contact lens wearers, excluding Biofinity habitual wearers, have at least 3 months of soft contact lens wearing experience, and who wear their habitual lenses at least 5 days per week and at least 8 hours per day.
 
[REDACTED]
 
[REDACTED]

Key inclusion criteria (See Section 8.1 for a complete list of inclusion criteria)	
 • Successful wear of spherical daily wear frequent replacement soft contact lenses for distance correction in both eyes during the past 3 months for a minimum of 5 days per week and 8 hours per day. • Manifest cylinder ≤ 0.75 D in each eye. • Best spectacle corrected visual acuity 20/20 or better in each eye. 
█ [REDACTED]
 
[REDACTED]

Table 3-1 Schedule of Study Procedures and Assessments

Procedure/ Assessment	Visit 1	Visit 2	Visit 3	Visit 4	Early Exit	USV
	Screening/ Baseline/ Dispense Day 1	Week 1 Follow-up Day 7	Month 1 Follow-up Day 30	Month 3 Follow-up/ Exit Day 95		
Informed Consent	✓	-	-	-	-	-
Demographics	✓	-	-	-	-	-
Medical History	✓	✓	✓	✓	✓	(✓)
Concomitant Medications	✓	✓	✓	✓	✓	(✓)
Inclusion/ Exclusion	✓	-	-	-	-	-
Habitual lens information (brand / manufacturer, modality, power, wear success, habitual lens care brand)	✓	-	-	-	-	-
[REDACTED]	■	■	■	■	■	■
[REDACTED]	■	■	■	■	■	■
[REDACTED]	■	■	■	■	■	■
[REDACTED]	■	■	■	■	■	■
[REDACTED]	■	■	■	■	■	■
[REDACTED]	■	■	■	■	■	■
Biomicroscopy ²	✓	✓	✓	✓	✓	(✓)
[REDACTED]	■	■	■	■	■	■
[REDACTED]	■	■	■	■	■	■
[REDACTED]	■	■	■	■	■	■
[REDACTED]	■	■	■	■	■	■
Randomize	✓	-	-	-	-	-
[REDACTED]	■	■	■	■	■	■

[Redacted]

[Redacted]

[Redacted]

[Redacted]

[Redacted]

[Redacted]

[Redacted]

[Redacted]

[Redacted]

[Redacted]

[Redacted]

[Redacted]

[Redacted]

[Redacted]

[Redacted]

[Redacted]

[Redacted]

[Redacted]

[Redacted]

[Redacted]

[Redacted]

[Redacted]

[figure not shown]
[Redacted]

[Redacted]

[Redacted]

[Redacted]

[Redacted]

5 INTRODUCTION

5.1 Rationale and Background

[Redacted text block]

[Redacted text block]

In this clinical study, the performance of the investigational [redacted] contact lens will be compared to the commercially available Biofinity contact lens in a parallel group design to demonstrate the safety and effectiveness of the [redacted] contact lens, worn daily [redacted] [redacted] as compared to Biofinity contact lens, worn daily [redacted] [redacted]. The intended use of this contact lens is for vision correction. Therefore, the measurement of distance VA is planned as the primary effectiveness [redacted]

[Redacted text block]

5.2 Purpose of the Study

The purpose of this clinical study is to demonstrate the safety and performance of the investigational [redacted] soft contact lens compared to the commercially available Biofinity soft contact lens.

At the end of the study, a clinical study report will be prepared in accordance with applicable regulatory requirements and standards.

[REDACTED]

5.3 Risks and Benefits

Contact lenses may offer improved peripheral vision and the convenience of not wearing spectacles. Material properties and design characteristics of [REDACTED] contact lenses are features consistent with successful contact lens wear. Based upon nonclinical testing and documented rationale for applicability of test results, [REDACTED] contact lenses are assessed to be non-toxic and biocompatible for on-eye use.

In the US, Biofinity contact lenses have approved indications for use for both daily wear and extended wear for up to 6 continuous nights. Further details on any known potential risks and benefits can be found in the product package insert.

A summary of the known potential risks and benefits associated with [REDACTED] contact lenses can be found in the IB. [REDACTED]

[REDACTED]

[REDACTED]

Refer to the IB for additional information.

6 STUDY OBJECTIVES

6.1 Primary Objective(s)

Table 6-1 Primary Objective(s)

Objective(s)	Endpoint(s)
Demonstrate noninferiority [REDACTED] compared to Biofinity in CLCDVA at Week 1 Follow-up.	Mean CLCDVA in each eye at Week 1 Follow-up.

6.2 Secondary Objective(s)

Table 6-2 Secondary Objective(s)

Objective(s)	Endpoint(s)
Demonstrate noninferiority [REDACTED] compared to Biofinity in the percentage of subjects achieving CLCDVA 20/20 or better in each eye, at Week 1 Follow-up.	Percentage of subjects achieving CLCDVA 20/20 or better in each eye at Week 1 Follow-up.

6.4 Safety Objective(s)

Table 6-3 Safety Objective(s)

Objective(s)	Endpoint(s)
Duty of care and evaluation of safety profile of the investigational products.	AEs Biomicroscopy findings Device deficiencies

